#### **1.0 INTRODUCTION**

Coversin is a small protein complement C5 inhibitor which prevents the cleavage of C5 by C5 convertase into C5a and C5b. It is effective in inhibiting terminal complement activity irrespective of the activating pathway. In *in vitro* experiments it has been found to be as effective as eculizumab (Soliris®) at a molar equivalent dose in preventing the haemolysis of affected clones of red blood cells taken from patients with paroxysmal nocturnal haemoglobinuria (PNH). Following an initial successful Phase Ia clinical trial in healthy human volunteers it is now being developed for the treatment of patients with PNH and other complement mediated diseases. Its small molecular size relative to the monoclonal antibody Soliris® makes it suitable for small volume subcutaneous injection with the advantage that patients can self-administer the drug and are not tied to bi-monthly intravenous infusions which necessitate either attendance at a hospital clinic or a home visit by a suitably qualified nurse.

Under this protocol named patients with PNH and proven resistance to eculizumab will be treated with Coversin for 6 months in order to determine the safety and efficacy of the drug in these circumstances. If satisfactory control of the PNH is achieved, and at the discretion of the PI, patients will have the option of remaining on Coversin and being entered into the long term follow-up study.

[figure not shown]
#### **1.1 Investigational Product**

Coversin sterile solution for subcutaneous injection 7.2 mg/ml [NB This is the concentration of the drug product (DP) to be used for the initial treatment of the first patient treated under this protocol. Coversin is still in development and this concentration may change. It is intended that fixed dosing for all patients between 50 and 100kg in weight will be introduced following Phase Ib clinical trials]

Coversin is a compact small protein molecule with a lipocalin-like structure consisting of alpha helices and a beta barrel. There is a surface active site which binds to the complement C5 molecule with a high affinity ( $K_D$  1.85 x 10-8) and an internalised active site which appears capable of binding small eicosinoid molecules such as leukotriene B4 [1]. The importance or otherwise of the latter site in the pharmacological and presumed therapeutic activity of Coversin has not been fully determined.

The molecular mass of Coversin as predicted by molecular modelling and confirmed by mass spectrometry is 16.7855 kDa.

The amino acid sequence of Coversin showing disulphide bridges is shown below:

Coversin drug substance is presented as a colourless aqueous solution stored frozen at -20°C. Coversin drug product is presented as a colourless aqueous sterile-filtered solution for injection in 2ml vials filled to 0.5ml at a concentration of 8.9mg/ml. It will be prepared for s.c. administration by drawing up the requisite volume to deliver the desired dose in one or more syringes. No more than 1.0ml will be administered to a single injection site because of potential discomfort. Doses will be adjusted to the subject's weight.

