**Principal PIs Signatures:** 

By my signature, I confirm that my staff and I have carefully read and understand this protocol and agree to comply with the conduct and terms of the study specified herein.

Signature:

[name] Radboud University Medical Centre Nijmegen Netherlands

Signature:

Mu

Date: 11 November 2015.

[name] Radboud University Medical Centre Nijmegen Netherlands

Protocol AK-Study-578 - version 2.0 11 november 2015

CONFIDENTIAL

© Akari Therapeutics Plc

Protocol synopsis				
Protocol Title:	Coversin in paroxysmal nocturnal haemoglobinuria (PNH) in patients with resistance to eculizumab due to complement C5 polymorphisms.			
Protocol Number:	AK Study 578			
Sponsor:	Akari Therapeutics Plc			
	[name]			
	[name]			
	UK			
Investigational Product(s):	Coversin (rVA576) sterile solution for subcutaneous injection 7.2 mg/mL			
Phase of Development:	П			
Indication:	Paroxysmal nocturnal haemoglobinuria			
PI(s):	[name]			
	[name]			
	Department of Haematology			
	Radboud University Medical Centre			
	Nijmegen			
	Netherlands			
Study Center(s):	Radboud University Medical Centre			
	Nijmegen			
	Netherlands			
Objectives:	Primary Objective: Safety of Coversin (rVA576).			
	Secondary Objectives: Efficacy of Coversin in the treatment of patients with PNH resistant to eculizumab.			
Study Design:	Open label, non-comparative			
Planned Number of Subjects:	Minimally 1 and maximally 6			
	Patients with PNH, male or female, 18 years or older with proven resistance to eculizumab due to complement C5 polymorphisms			
Subject Population:				
Subject Population: Diagnosis and Main				
Diagnosis and Main Criteria for Inclusion and	resistance to eculizumab due to complement C5 polymorphisms			
Diagnosis and Main	resistance to eculizumab due to complement C5 polymorphisms Inclusion Criteria:			
Diagnosis and Main Criteria for Inclusion and	
 
resistance to eculizumab due to complement C5 polymorphisms
 
Inclusion Criteria:
 
Patients with known paroxysmal nocturnal haemoglobinuria (PNH)
 
			

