#### 6.0 TRIAL PROCEDURE

The trial will comprise an open label, non-comparative study of minimally 1 patient and maximally 6 patients with PNH and known resistance to Eculizumab, who meet the inclusion and exclusion criteria (see below). Patients agreeing to participate in the trial will be admitted to the hospital for a minimum of 2 days for initiation of Coversin treatment, for clinical observation and for bloodsampling (PK/PD). Treatment will be continued on an out-patient basis with daily visits until stabilization or adjustment of dose.

Patients deemed capable of self-administration will be taught how to calculate and draw up the appropriate volume of solution for injection and how to inject subcutaneously. They will also be taught how to store and thaw Coversin prior to injection.

For Patients deemed not capable of self administration, alternative facilities for administration at home will be sought (General Physician or suitably qualified home care nurse).

Only if, in the opinion of the PI, the patient is capable of self injecting the correct dose of Coversin or adequate alternative facilities existfor safety monitoring and dosing supervision, treatment will be transferred to admisitration at home.

If not already immunised against *Neisseria sp.* immunisation and prophylactic antibiotics will be administered as set out in Section 10 below. Nose and throat swabs will be taken although growth of *Neisseria* species will not be grounds for exclusion but will prompt particular vigilance on the part of the PI.

The ablating dose will be divided between as many injection sites as are necessary to avoid injection of >1.2mL of Coversin solution for injection. These sites may be chosen from the deltoid regions, the anterior abdominal region or the anterior femoral regions. The injection sites used will be recorded in the patient notes and will be inspected at 24 hour intervals for 5 days for injection site reactions.

Doses of Coversin will be given at the same time each day, preferably between 6 and 8am. The time of each dose will be recorded in the CRFs. Patients self-administering Coversin will use suitable sites on the anterior femoral and anterior abdominal regions and the site, date and time of injection will be entered on the appropriate CRF sheet (patient diary) and be initialled by the supervising nurse.

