#### 6.2 Description of Trial Treatments, Dosage and Dosage Regimens

Coversin for subcutaneous injection will be supplied initially as vials of frozen solution, each 2mL vial containing 1.2mL of 7.2mg/mL solution. Vials should be stored frozen at  $-20^{\circ}$ C until between 12 and 24 hours of use when they should be allowed to thaw at ambient or refrigerated (2 – 6°C) temperature. Ideally they should be thawed overnight in refrigerated conditions.

Following the initial batch for use in the first patient treated under this protocol it is likely that all future batches will be supplied as lyophilised powder 15mg in 5mL glass vials. Until reconstituted it can be stored at ambient temperature for the duration allowed by the expiry date printed on the label. It will be reconstituted within 6 hours of administration with 0.5mL of sterile water for injection to form a solution of 30mg/mL concentration. After injection of

sterile water into the Coversin vial it should be shaken a few times until no particulate matter remains. After reconstitution vials should be stored between 2 and 6°C until used and in any case for no longer than 24 hours.

Following the switch to lyophilised powder the maintenance dose will be changed to a fixed multiple of 15mg (ie 15, 30 or 60mg) which will be the next dose above the dose that the patient is being maintained on. Thereafter the first ablating dose in all future patients treated under this protocol will be 60mg (2mL) which will divided between two injection sites.

After the first, ablating, dose all subjects will receive fixed daily maintenance doses for the remainder of the trial. The size of the fixed maintenance dose will be determined by the results achieved in the first patient treated under this protocol. As mentioned above there will be some flexibility to allow for adjustment of dose in individual patients if they do not appear to be responding adequately but the overall aim will be to find a fixed dose that will maintain full complement inhibition in all patients treated.

All doses should be given at the same time each day, ideally between 6 and 8 am. Blood samples should be taken immediately pre-dose or as shown in appendix 1.

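### The liquid drug product has two concentrations and fills (7.2 mg/mL in 1.2 mL; 8.9 mg/mL in 0.5 mL), and the limit per injection site is 1.0 mL or 1.2 mL

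*Combined protocol and SAP*

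**What the plan says.** **Concentration and fill.** The synopsis lists the product as a "sterile solution for subcutaneous injection 7.2 mg/mL" and gives no fill volume. Section 1.1 opens with the same 7.2 mg/mL. A bracketed note ties that figure to the initial treatment of the first patient and warns that it may change. The last paragraph of Section 1.1 then describes the drug product, in the present tense, as "2ml vials filled to 0.5ml at a concentration of 8.9mg/ml", and goes straight on to how the volume for a dose is drawn up. Section 6.2 describes the initial frozen supply as "each 2mL vial containing 1.2mL of 7.2mg/mL solution". It expects later batches to be a lyophilised powder made up to 30 mg/mL.

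**Volume per site.** Section 1.1: "No more than 1.0ml will be administered to a single injection site". Section 6.0 divides the ablating dose over enough sites "to avoid injection of >1.2mL of Coversin solution for injection".

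**Who works out the volume.** Under Section 6.0, patients thought able to self-inject are "taught how to calculate and draw up the appropriate volume of solution for injection".

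**Time after reconstitution (powder only).** Section 6.2 says "It will be reconstituted within 6 hours of administration". It then allows refrigerated storage until use, "in any case for no longer than 24 hours".

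**The concern.** Concentration is the one figure that turns a dose in mg/kg into a volume in a syringe. Hospital staff use it at initiation, and patients who self-inject may use it at home. Section 1.1 gives two values a few lines apart, and the second comes directly before a preparation instruction, so it cannot be set aside as background. The note that the concentration may change does not explain 8.9 mg/mL, because no batch, patient or date is attached to that value. The next formulation that the protocol describes is 30 mg/mL.

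What is at stake is knowing the dose received. Section 6.0 titrates the maintenance dose on CH50 and LDH, and Section 6.2 bases the fixed maintenance dose for later patients on the first patient's results. For home injections, Section 6.0 has the diary record site, date and time. The text does not ask for the volume injected or the concentration on the label. The compliance check in Section 11.0 counts used vials, and what a vial contains depends on which description applies.

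**Working it through.** **Inputs**
- Concentration: 7.2 mg/mL (synopsis, Section 1.1 opening, Section 6.2) and 8.9 mg/mL (Section 1.1, last paragraph).
- Fill: 1.2 mL (Section 6.2) and 0.5 mL (Section 1.1).
- Limit per site: 1.0 mL (Section 1.1) and 1.2 mL (Section 6.0).
- Ablating dose 0.57 mg/kg and first maintenance dose 0.14 mg/kg (Section 3.0).
- Body weight 70 kg, as an illustration within the 50 to 100 kg range of Section 9.1.

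**The protocol's own related figures reproduce**
- Powder: 15 mg / 0.5 mL = 30 mg/mL, and 60 mg / 30 mg/mL = 2 mL, as Section 6.2 states.
- Maintenance: 25% × 0.57 = 0.1425 mg/kg, shown as 0.14.

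**Relative error if the figure used does not match the vial** (independent of body weight)
- Volume worked out at 8.9, vial holds 7.2: 7.2 / 8.9 = 0.809, so 19% below the intended dose.
- Volume worked out at 7.2, vial holds 8.9: 8.9 / 7.2 = 1.236, so 24% above it.
- A nominal 0.57 mg/kg becomes 0.461 or 0.705 mg/kg. A nominal 0.14 mg/kg becomes 0.113 or 0.173 mg/kg.

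**At 70 kg: volume = weight × dose / concentration; sites = volume / limit, rounded up**

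| | Dose | Concentration | Volume | Sites at 1.0 mL | Sites at 1.2 mL |
|---|---|---|---|---|---|
| Ablating | 70 × 0.57 = 39.9 mg | 7.2 mg/mL | 5.54 mL | 6 | 5 |
| Ablating | 39.9 mg | 8.9 mg/mL | 4.48 mL | 5 | 4 |
| First maintenance | 70 × 0.14 = 9.8 mg | 7.2 mg/mL | 1.36 mL | 2 | 2 |
| First maintenance | 9.8 mg | 8.9 mg/mL | 1.10 mL | 2 | 1 |

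**Content of a vial**
- 1.2 × 7.2 = 8.64 mg; 0.5 × 8.9 = 4.45 mg; ratio 8.64 / 4.45 = 1.94.
- Vials for 39.9 mg: 39.9 / 8.64 = 4.62, so 5; 39.9 / 4.45 = 8.97, so 9.
- Vials for 9.8 mg: 9.8 / 8.64 = 1.13, so 2; 9.8 / 4.45 = 2.20, so 3.

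**Powder phase.** A 60 mg dose is 2 mL in two sites, or 1.0 mL each, which meets both limits. The conflict over site volume affects only the frozen solution.

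**The case against.** The strongest reply is that nobody need ever use the wrong figure. The synopsis, the note in Section 1.1 and Section 6.2 agree on 7.2 mg/mL for the initial supply, and the 8.9 mg/mL sentence is a general product description that names no batch. The person drawing up a dose would be expected to read the vial. The ablating dose is given during the initial hospital admission, and home dosing requires the investigator to be satisfied that the patient can inject the correct dose or that adequate alternative arrangements exist. Coversin levels are also measured (Section 11.1), and used vials and syringes are counted in the first month at home (Section 11.0). The frozen, weight-based phase initially concerns one patient.

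Most of this stands as a limit on the consequence. The documents do not show the label of the frozen vial or the patient instructions, so the 19% and 24% are conditional. It is also fair that the site count matters mainly for the ablating dose: at 7.2 mg/mL the 70 kg first maintenance dose needs two sites under either limit.

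It does not remove the contradiction. No text assigns 8.9 mg/mL anywhere, and the limits of 1.0 and 1.2 mL cannot both be the rule for the ablating dose of frozen solution. The vial count is a weaker safeguard than it looks, because converting vials to mg needs the fill and concentration that are in conflict.

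The 6-hour and 24-hour wording is a softer matter. It can be read as a preparation target followed by an outer storage limit, so it is ambiguous rather than clearly contradictory. It concerns the powder and has no bearing on the 19% and 24%.

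**Conclusion.** The inconsistency is real and should be corrected. The liquid product has two concentrations, 7.2 and 8.9 mg/mL, and two fills, 1.2 and 0.5 mL. The limit per site is 1.0 or 1.2 mL. If a volume is worked out from the figure that does not match the vial, the delivered dose is 19% low or 24% high at any body weight. The 70 kg volumes are illustrations. Confidence is high for the conflict in the text. The consequence is potential and confined to the frozen-solution, weight-based phase.

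Three stronger readings are tempting, and the documents do not support them:
- **That patients will be misdosed by 19% to 24%.** This needs someone to use a figure that does not match the vial, and correct labelling may prevent it. Nor is it shown that both figures describe the same supply; what is shown is that 8.9 mg/mL is left unassigned.
- **That a planned dose-response result is confounded.** The objectives in Section 2.0 are safety, and whether the regimen controls the disease. Section 13.1 contains no dose-response analysis. The narrower point is that received mg could be uncertain in a trial of one to six patients.
- **That a single concentration should appear throughout.** Section 6.2 also describes a 30 mg/mL reconstituted product, so the requirement is one concentration and fill for each formulation.

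**What to change.** Reconcile the synopsis and Sections 1.1, 6.0 and 6.2 so that each named formulation (frozen solution, lyophilised powder) has one stated concentration and one fill. If 8.9 mg/mL belongs to a particular batch, name the batch; if not, remove the conflict. State one volume limit per site and use it in both Section 1.1 and Section 6.0. In the same edit, say how the 6-hour and 24-hour statements in Section 6.2 relate to each other. This review takes no position on which concentration, fill, volume or time limit is right; that is for the sponsor and the investigator.

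Optionally, have the diary record the labelled concentration and the volume injected for each dose, so that the mg received can be derived and vial counts checked against it.

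The cost is a correction to the protocol text plus, if the option is taken, one or two diary fields. Sample size, visits and the planned analyses do not change.

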## **1.2** Summary of Nonclinical and Clinical Studies Relevant to the Clinical Trial

Coversin is a recombinant small protein (MW 16.8kDa) which is derived from a native protein discovered in the saliva of the *Ornithodoros moubata* tick [2]. Its function in tick saliva is to assist the parasite in feeding by suppressing the host immune reactions that would otherwise alert the host to the presence of the parasite which could then be removed by scratching or grooming. It has been known for some time that all species of ticks, which can feed undisturbed on their hosts including rodents, cattle, dogs and man, for periods of 14 days or more, secrete an array of immunomodulatory peptides and proteins in their saliva in order to take control of their hosts' local and systemic immune and inflammatory responses [3].

The complement system is an important part of the innate immune system in many animal species including all mammals. There are three known pathways in the cascade: the classical, the alternative and the lectin but all converge on a final common pathway. At this point complement C5, a product of the classical pathway is acted upon by the enzyme C5 convertase, a product of the alternative pathway, to form C5a and a cluster of proteins (C5b, C6, C7, C8, and C9) which are collectively known as the membrane attack complex (MAC). It is known that many human autoimmune diseases are associated with inappropriate reactions to products of the final common pathway of the complement system. In particular myasthenia gravis, in which individuals form antibodies to their own acetyl choline receptors (approximately 70% of all MG patients) is associated with either inappropriate reaction to or over-production of MAC proteins [4].

[figure not shown]
CONFIDENTIAL

Coversin binds to the C5 molecule, preventing any C5 convertase from acting on it and cleaving it to form C5a and the MAC. It appears to do this by interfering with the interaction of C5 convertases rather than by blocking the actual cleavage site on the C5 molecule [5]. The binding to C5 is high affinity ( $K_D$  1.85 x 10^-8) and appears to be irreversible in physiological conditions [6]. Other studies including X-ray crystallography have confirmed that Coversin complexes with human complement C5 [5].

Inhibition of the C5 complement system is a therapeutic target in a wide range of autoimmune and inflammatory diseases including rheumatoid arthritis, Crohn's disease, hypersensitivity pneumonitis, ischaemia reperfusion injury, sepsis, myasthenia gravis, paroxysmal nocturnal haemoglobinuria (PNH) and age related macular degeneration [7-14].

[figure not shown]
The initial proposed clinical indication is PNH in patients known to be resistant to eculizumab because of polymorphisms occurring in the complement C5 molecule. The humanised monoclonal antibody eculizumab (Soliris®) was approved in Europe and the USA for the treatment of PNH in 2007 and is now the standard of care in this condition. Since Coversin acts in exactly the same way as Soliris® it is believed that it will be effective as a therapeutic agent in the treatment of PNH but may offer patient benefits in terms of convenience since it can be self-administered by sub cutaneous injection rather than having to be administered by a health-care professional by intravenous infusion at two weekly intervals and in addition can be used in patients resistant to eculizumab.

[figure not shown]
There are no satisfactory animal models of PNH and the presumed efficacy of Coversin in this condition relies on the fact that, since its mode of action is identical to that of Soliris® with the exception that it binds to a different epitope on the C5 molecule, the clinical effects on patients with PNH are likely to be the same. In addition Coversin has been tested in an *in vitro* flow cytometry model using blood from patients with PNH with a large clone of Type III PNH cells . In this model the blood was either complement inactivated through heat treatment (negative control) or not and complement activation was achieved by acidification and the addition of magnesium chloride (MgCl). Blood so treated was first spiked with either Coversin or Soliris® in ascending concentrations and the effect of complement activation on the relative populations of Clone III to Clone I RBCs was observed. These results are shown in Figs 1 and 2 below. They show that Coversin 10µg/mL and Soliris® to 20µg/mL (molar equivalent concentrations) are equally effective in preventing haemolysis in blood from a patient with Type III red blood cells These results are illustrated below in Figs 1 and 2.

Complement activation by MgCI results in depletion of clone III red cells and increase in Clone I Addition of Coversin increases Clone III up to max ~20mcg/ml

## Fig 1 Effect of ascending concentrations of Coversin on complement activation in blood from a patient with PNH and type III PNH erythrocytes only.

[figure not shown]

[figure not shown]

## 1.3 Summary of Known and Potential Risks and Benefits to Human Subjects

Although there has been limited clinical experience with Coversin to date the clinical implications of complement C5 blockade can be deduced from a combination of genetic and epidemiological studies, animal studies and experience with eculizumab (*Soliris*®), an anti-complement C5 monoclonal antibody. Complement C5 deficiency in humans is a rare, familial condition caused by a variety of genetic defects including mutations in the C5 exons. Those affected have a predisposition to gram negative infections, particularly meningococcal meningitis, herpetic infections and seborrhoeic dermatitis. [17]

In clinical trials of eculizumab in paroxysmal nocturnal haemoglobinuria (PNH) 2 of 96 patients developed meningococcal meningitis and currently all subjects taking the drug are advised to maintain *Neisseria meningitidis* immunization with booster shots at recommended intervals. [18] In limited duration toxicological studies with both eculizumab and Coversin no adverse events or findings attributable to C5 blockade have been reported but PIs are advised to be alert for possible infectious events even in subjects who have received meningococcal immunisation. All subjects screened for entry into this trial will have pre-trial throat and nasal swabs taken within 5 days of entry and any positive *Neisseria sp.* results will be grounds for excluding that subject from the trial irrespective of immunisation status until the bacteria have been eliminated.

In long term studies and post marketing surveillance of eculizumab patients for periods in excess of three years, apart from the increased risk of meningococcal infection referred to above, the most commonly reported side effects were headache, runny nose (nasopharyngitis), back pain, nausea and tiredness (fatigue). However these are all known to be associated with the use of antibodies rather than any known association with complement inhibition and, in any case, in trials the incidence was not significantly different from symptoms experienced by placebo treated patients.

There have been no adverse events in single or repeat dose animal toxicology studies of Coversin in doses up to 100 times the anticipated human dose. It is not anticipated that there will be any difference in the risk or adverse event profile of Coversin compared to eculizumab.

Because Coversin is a xenologous protein (derived from a tick salivary protein) there is always a possibility that its chronic use may be associated with the formation of antibodies which could neutralise the effect of the drug or cause untoward adverse reactions. The immunogenicity study mentioned above has gone some way to mitigating this possibility and experience with other parasite derived therapeutic molecules such as the leech-derived anticoagulant lepirudan suggest that parasite derived therapeutic molecules are not usually associated with neutralising activity.

Potential benefits to patients with autoimmune disease remain to be evaluated but it is anticipated on the basis of results in animal models considered to be predictive of human disease that patients with autoimmune neurological conditions in which one or more specific antibodies to target tissues have been identified and which are known to be associated with complement activation will benefit from C5 inhibition. Such conditions include myasthenia gravis, Guillain Barré syndrome and varieties of multiple sclerosis associated with the MOG16 antibody.

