#### 9.1 Inclusion Criteria

- Males or females taking adequate contraceptive precautions if of childbearing potential, 18 80 years of age
- Body weight  $\geq$ 50kg and  $\leq$  100kg
- The patient has provided written informed consent.
- Willing to avoid prohibited medications for duration of study (see Exclusion Criteria)
- Must agree to take appropriate prophylactic precautions against Neisseria infection
- Must be counselled regarding the possible reproductive risks of using Coversin and be advised to use an adequate method of contraception pending further data on reproductive toxicology.

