#### 10.0 NEISSERIA IMMUNISATION AND ANTIBIOTIC PROPHYLAXIS

It is known that the products of C5 complement activation are important in protection against infection by *Neisseria* species (15). This is believed to be the only known hazard of blocking this stage of the complement cascade and patients taking part in previous trials of complement C5 inhibitors were found to be at greater risk of *Neisseria* infection, particularly meningococcal infection (16). For this reason all patients entering the trial should where possible have received immunization against *Neisseria meningitidis* infection in the past, or must receive a booster shot of quadrivalent vaccine (against meningococci type ACW135Y) ) at the time of recruitment into the trial and at least prior to receiving the first dose of medication. In addition all patients should be immunised against Meningitis B using the *Bexsero*® vaccine as soon as this vaccine is available in the country where the patient is treated. This vaccine requires an initial dose followed by a booster 1 month later.

All patients will in addition have throat and nasal swabs taken after entry to the trial and prior to receiving the first dose. Cultures positive for any *Neisseria* species will not be grounds for excluding that subject from the trial but will alert the PI to use extra vigilance during and after induction of complement inhibition. Any patient having positive nasal swabs will be retested 7 days later to ensure that the pathogen has been eliminated by ciprofloxacin.

Patients will preferably receive a 5 day course of oral ciprofloxacin commencing the day before the first dose of Coversin and this will either be followed by oral penicillin prophylactic treatment or, at the discretion of the PI and in accordance with local custom, the patient may be provided with high dose ciprofloxacin to be started in the event of an actual or suspected infection. Patients will be instructed to make urgent contact with the PI or her deputy in that event.

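### Section 1.3 bars a Neisseria-positive patient until clearance, Sections 6.0 and 10.0 say a positive culture does not exclude, and no visible eligibility list settles it

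*Combined protocol and SAP*

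**What the plan says.** Section 1.3 has everyone screened swabbed in the throat and nose before the trial, within 5 days of entry. It then says that any positive Neisseria "results will be grounds for excluding that subject from the trial irrespective of immunisation status until the bacteria have been eliminated".

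Section 6.0 also calls for nose and throat swabs, but says that growth of Neisseria "species will not be grounds for exclusion but will prompt particular vigilance on the part of the PI".

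Section 10.0 agrees with 6.0: a culture positive for any Neisseria "species will not be grounds for excluding that subject from the trial but will alert the PI to use extra vigilance". It says when that vigilance applies: the positive culture "will alert the PI to use extra vigilance during and after induction of complement inhibition". It adds a retest: "Any patient having positive nasal swabs will be retested 7 days later to ensure that the pathogen has been eliminated by ciprofloxacin". On the antibiotic it says: "Patients will preferably receive a 5 day course of oral ciprofloxacin commencing the day before the first dose of Coversin".

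In the eligibility lists, the only Neisseria item in Section 9.1 is "Must agree to take appropriate prophylactic precautions against Neisseria infection". Section 9.2 lists body weight and pregnancy. The visible synopsis criteria have no swab item; the nearest is the investigator's general judgement of fitness.

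**The concern.** The three sections deal with the same swab sites and the same organism and give opposite consequences. Entering a patient before clearance breaches Section 1.3. Refusing entry because of the swab contradicts 6.0 and 10.0.

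The subject is not minor. Section 10.0 says of susceptibility to Neisseria: "This is believed to be the only known hazard of blocking this stage of the complement cascade". Section 1.3 reports meningococcal meningitis in 2 of 96 patients (2/96 = 2.1%) in the eculizumab PNH trials and expects no difference in Coversin's risk profile. A reader who judges risk from Section 1.3 would count clearance before entry as a safeguard. Staff working from 6.0 and 10.0 are not told to require it.

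There is a smaller consequence for the analysis. Section 13.6 limits efficacy data to measurements made while the protocol was correctly followed. For a patient entered while swab-positive, whether that holds could depend on which section is read.

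**Working it through.** The plan states no figure to reproduce here. The check is a comparison of text.

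**Step 1. The three sections side by side**

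| | 1.3 | 6.0 | 10.0 |
|---|---|---|---|
| Sites swabbed | throat, nose | throat, nose | throat, nose |
| Timing | pre-trial, within 5 days of entry | not stated in the sentence | after entry, before first dose |
| Positive result | excluded until eliminated, whatever the immunisation status | not excluded; vigilance | not excluded; vigilance |
| Retest | not described | not described | 7 days later, nasal swabs only; no action given if still positive |
| Clearance required before entry or dosing | yes | no | no |

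Count: 1 section excludes, 2 do not.

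**Step 2. Can the sections be read together?**

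*As different swabs.* The timing wording differs, but 6.0 does not limit its statement to swabs taken after entry, and 10.0 says the patient is not excluded from the trial. Entry is not defined in the visible text and Appendix 1 is not visible. The timing is therefore a mismatch to clear up, not a proven clash.

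*As a temporary bar that the 10.0 retest lifts.* Count the first dose as day 1, as in Section 3.0.
- On the preferred timetable ciprofloxacin starts on day 0. Five days run from day 0 to day 4, so the course ends after dosing has begun.
- Assume the 7 days run from the swab. A swab taken d days before the first dose is retested 7 − d days after that dose. The retest falls on or before the first dose only if d ≥ 7, and Section 10.0 sets no such minimum.
- On the preferred timetable, a retest done before the first dose would follow at most one day of ciprofloxacin.

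Section 10.0 therefore allows dosing before elimination is confirmed. Section 1.3 does not allow even entry.

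**Step 3. Do the eligibility lists settle it?**

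Swab criterion in the visible synopsis criteria: 0. In Sections 9.1 and 9.2: 0. So 0 of 2 visible lists has one. No visible text gives one section precedence over another.

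**Step 4. Separate, lower-grade note**

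Section 6.0 sends the reader to the criteria further down. The synopsis has 3 exclusions: pregnancy, tick or arthropod-venom allergy, and investigator-judged unfitness. Visible Section 9.2 repeats 1 of them (pregnancy), so 3 − 1 = 2 are not there. The LDH threshold of 1.5 ULN and the specific test for eculizumab resistance are also not visible in Section 9.

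**The case against.** The strongest reply is that the two procedural sections agree, and the outlier is one sentence in an introductory risk summary. A single centre with at most 6 patients would probably follow the procedural text, and perhaps no patient will be swab-positive. Other protection is also planned: ACW135Y vaccination, antibiotic cover when vaccination is recent, penicillin or stand-by ciprofloxacin, and urgent contact with the investigator. Section 10.0 does order a retest.

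Some of this stands:
- The number affected may be zero.
- The other safeguards bear on how serious the consequence would be.
- The vigilance wording in 10.0 could also describe a patient who was positive and has since cleared. The firm statement is that 10.0 permits induction without confirmed clearance.
- An investigator could choose to wait for clearance under 10.0.
- The hazard statement in 10.0 is hedged as a belief.
- The text is incomplete: the synopsis table is broken, and Section 9.1 points to prohibited medications in exclusion criteria that do not show them. Statements about the lists therefore apply to visible text only.

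None of this removes the conflict. Section 1.3 is written as an instruction, not as background. A two-to-one count does not cancel it, and the retest is not a condition for entry or dosing. A rule in Appendix 1 would still leave the three sections contradicting each other.

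**Conclusion.** The concern holds, with high confidence. The protocol is wrong as written on this point and must be corrected, because the conflict decides who may enter and when, under the main infection risk the protocol identifies. One section bars a swab-positive patient until clearance, two do not, and 0 of 2 visible eligibility lists resolves it. It affects any swab-positive patient among the 1 to 6 planned, so between 0 and 6 of those enrolled.

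The contradiction rests on the wording alone. The retest timeline also assumes that the 7 days run from the swab. The differences between Section 9 and the synopsis are a separate, lesser matter and add no weight to this conclusion.

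**What to change.** Reconcile Sections 1.3, 6.0 and 10.0. This review does not say which rule is right; that is for the sponsor and investigators.

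- State one rule for a positive swab, in identical words in all three sections and in the eligibility criteria (synopsis and Section 9).
- State one swab timing and define entry.
- Say whether the retest covers throat as well as nasal swabs, whether its result is needed before the first dose, and what follows if it is still positive.

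The cost is protocol wording. Depending on the rule chosen, swab-positive patients may enter later, or a throat-swab retest may be added.

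Separately and at lower priority, align Section 9 with the synopsis. Someone checking eligibility from the visible Section 9 alone is not prompted to ask about tick or venom allergy, although the drug is derived from a tick protein.
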